3. To measure VE using other outcome measures such as against all episodes of *Pf malaria with symptoms* and *Pf malaria* rather than against the first episode, using proportional analysis, or using ITT or ATP populations, or severity of malaria infections or hemoglobin concentration.
4. To explore the relationship between detectable parasitemia prior to vaccination and VE.

Endpoints:

Primary Endpoints:

1. Proportion of vaccinees compared to controls experiencing related SAEs from V1 to 26 weeks after V3
2. VE computed as one minus the estimated hazard ratio (HR) (time-to-event analysis) for first episode of *Pf malaria with symptoms* from 2 weeks after V3 to 26 weeks after V3 in the modified ITT (mITT) population.

Secondary Endpoints:

1. Safety and tolerability in children
 - The differences in proportions of vaccinees compared to controls experiencing unsolicited AEs from the time of V1 to 14 days after V3 (or last immunization).

- The differences in proportions of vaccinees compared to controls experiencing laboratory abnormalities from time of V1 to 14 days after V3.
- The differences in proportions of vaccinees compared to controls experiencing solicited Aes during the 7 days following each immunization.
- 2. VE computed as one minus the estimated hazard ratio (HR) for first episode of *Pf malaria* detected by thick blood smear (TBS), from 2 weeks after V3 to 26 weeks after V3 in the mITT population.
- 3. Antibody levels to PfCSP by standardized ELISA comparing protected and unprotected vaccinees and controls.

Exploratory Endpoints:

- 1. Humoral and cellular immune responses to PfSPZ Vaccine
- 2. Genotyping of peripheral blood Pf parasites
- 3. Additional measures of VE
 - VE against all episodes (rather than first episode) of *Pf malaria with symptoms* and *Pf malaria* by Cox regression analysis
 - VE computed by proportional (binary) analysis (1 – risk ratio) for first episode of *Pf malaria* detected by TBS, from 2 weeks after V3 to 26 weeks after V3 in the intention-to-treat (ITT), mITT and according to protocol (ATP) populations (whole group and subgroups)
 - VE computed as one minus the estimated HR for first episode of *Pf malaria* detected by TBS, from 2 weeks after V3 to 26 weeks after V3 in the ITT and ATP populations (whole group and subgroups)
 - VE for *Pf malaria* measured by and nucleic acid detection in children from 2 weeks after V3 to 26 weeks after V3 using both (time to event, proportional/binary)

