2.3 SCHEDULE OF ACTIVITIES (SOA)

The schedule of assessment activities is detailed in **Erreur ! Référence non valide pour un signet.** and

Clinic Visits	1	2	3	4	5	6	7	8	9	10	11	12	13	14	15	Unscheduled Visit
Study Day	-73	-17	-16	-15	1	3	8	10	(12) ^M	(13) ^M	(14) ^M	22	29	32	36	NA
Days post PfSPZ Vaccination #1	-	-	-	-	0	2	7	9	11	12	13	21	28	31	35	NA
Days post last PfSPZ Vaccination	-	-	-	-	0	2	0	2	4	5	6	14	0	3	7	NA
Visit window (days)	→	-24/+10	→	→	0	+/-1	-1/+3	-1/+3	+/-1	→	→	+/-3	+/-3	+/-1	+/-2	NA
	Screening	Enrollment and AL dose	AL dose	AL dose	PfSPZ Vac #1	Safety t/u	PfSPZ Vac #2	Safety t/u	AL dosing	AL dose	AL dose	Pre-Vac	PfSPZ Vac #3	Safety t/u	Interim Clinical OR Positive t/u visit	
CLINICAL PROCEDURES																
Complete medical history/physical	X															
Informed consent	X															
Malaria comprehension exam	X															
Pre-test/ post-test HIV counseling	X															
Interim clinical evaluation	X	X	X	X	X	X	X	X	(X)	(X)	(X)	X	X	X	X	
AE/ SAE assessment	X	X	X	X	X	X	X	X	(X)	(X)	(X)	X	X	X	X	
Solicited Local/ Systemic AEs ^A									(X)	(X)	(X)	(X)	X	X	X	
Conned review	X	X	X	X	X	X	X	X	(X)	(X)	(X)	X	X	X	X	
ECG - Cardiology	X															
Treatment with AL ^B		X	X	X					(X)	(X)	(X)					
PfSPZ Vaccination or Placebo					X		X					X				
LABORATORY PROCEDURES	Tube type^C	Designated laboratory														
Screening/ safety labs																
CBC with differential	EDTA	MRTC (CPA/UB/ LPD)	0.5 ^I		(0.5) ^I		0.5					0.5				
ALT, Cr	SST		0.5 ^I		(0.5) ^I		0.5					0.5				
HBs, HCV, HIV testing	SST		5													
Malaria infection assays																
Retrospective Peripheral blood smear ^{C,D}	EDTA	MRTC (CPA/UB/ LPD)		0.5		0.5		0.5				0.5	0.5			(0.5) ^{D,I}
Retrospective qPCR ^D	EDTA	LMIV	0.5	0.5		0.5		0.5				0.5	0.5			(0.5) ^{D,I,11}
Research assays^E																
Humoral assays ^F	SST			5								5				
Cellular assays ^G	NaHep			5								5	10			
Transcriptional assays	PAXgene/ Nucleic Acid Stabilizer	LMIV/ MRTC (CPA/UB/LPD)		1		1						1	1			
Parasite purification	EDTA															(4) ^H
Ex vivo	EDTA (pediatric)			0.5								0.5	0.5			(0.5) ^{I3}
Estimated Maximum Daily Total^{I4}	6.5	12.5	0	0	3	0	2	0	0	0	0	13.5	1	11.5	0	5.5
Estimated Maximum Study Cumulative Total	6.5	19	19	19	22	22	24	24	24	24	24	37.5	38.5	50	50	NA
A) Systemic and Local reactogenicity related to PfSPZ Vaccination will be collected for 7 days after administration of PfSPZ Vaccine/Placebo.																

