B) AL dosing to occur AFTER labs collected																
C) Blood smear will be run Real Time for symptomatic subjects																
D) If a Blood smear (BS) is collected at an unscheduled visit due to suspected malaria, a sample for retrospective malaria qPCR should also be obtained at the same time (beginning after vaccination #1)																
E) On days where multiple research assays are collected, if unable to obtain blood for all samples, collection should be prioritized in the following order: 1) Humoral, 2) Transcriptional, 3) Ex-vivo, 4) Cellular. If research blood draws are not fully completed this will not be considered a protocol deviation.																
F) For humoral assays, 2-5mls can be collected based on investigators discretion.																
G) For cellular assays, 5-10 mls can be collected based on investigators discretion.																
H) ≤ 15ml of blood should be drawn per day in total; volume amounts per tube are estimates																
I) If clinically indicated																
J) Starting after vaccination #1, if the subject has malaria symptoms AND has a positive blood smear (BS) then he/she should return within 48 hours from draw of positive BS for additional sample collection, as needed (ex-vivo, transcriptional assay, qPCR). Subjects/guardian may decline to return for additional blood draw (not a protocol deviation). Preference will be to obtain BS positive blood samples for the FIRST positive smear after vaccination #3, >14 days post antimalarial treatment, new positive BS after having a negative BS >28 days.																
1) qPCR to be collected at unscheduled malaria positive BS visit if sample not obtained within the last two days with the positive blood smear																
2) parasite purification should be collected at unscheduled malaria positive BS visit if not collected in the last 28 days. If collected in the last 28 days, this 4ml collection can be deferred.																
3) ex-vivo to be collected at unscheduled malaria positive BS visit if sample has not been completed in the previous 2 days.																
K) Tube types listed in this table may be substituted for acceptable alternatives if the PI and the leads of the immunology and/or clinical labs (as applicable) agree to the change. Any substitutions will be documented in lab logs.																
L) These labs will be repeated prior to V1 if drawn 28 days or more before V1 is scheduled																

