- Five percent or more of the vaccinees enrolled at any time point in one arm (calculated as 5% of the vaccinees in the full study roster enrolled to date, as long as there are at least three subjects with the AE) experience the same severe (grade 3) AE during the periods of AE collection deemed possibly, probably or definitely related to study product administration (PfSPZ Vaccine or NS), or experience the same grade 3 laboratory abnormality on day V2 + 14 or day V3+14. Grade 3 AEs deemed possibly, probably or definitely related to malaria (as opposed to PfSPZ Vaccine or to NS) will not count toward meeting this criterion. The site, where clinical staff are blinded, can only monitor total populations (vaccine plus placebo recipients) and if a 5% threshold is reached, unblinded study staff (e.g., the head of Pharmaceutical Operations) will need to confirm that the total indeed constitutes 5% of vaccinees. Note that we have considered using Grade 2 rather than Grade 3 laboratory abnormalities, but drops in hemoglobin, neutrophils, platelets and sometimes other blood count indices meeting Grade 2 criteria for severity are common in African pediatric populations.
- One participant experiences an SAE deemed possibly, probably or definitely related to study product. This criterion will not be met if it turns out that the participant received NS. SAEs related to malaria or to antimalarial treatment which are expected, will be reported expeditiously but will not fulfill this criterion. If the SAE is unexpected with respect to malaria or antimalarial treatment, it will fulfill the criterion.

If either of these criteria appear to be met by ongoing surveillance at the site, the principal investigator will engage the head of Pharmaceutical Operations on site, or his/her designee, to

follow unblinding procedures (see **Section 6.3.3** for a description). To meet the criteria, the subjects must actually have received PfSPZ Vaccine and not NS placebo.

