9.11.4 Time Period and Frequency for Event Assessment and Follow-Up

The occurrence of an adverse event (AE) or serious adverse event (SAE) may come to the attention of study personnel during study visits and interviews of a study participant presenting for medical care, or upon review by a study monitor.

All AEs including local and systemic reactions not meeting the criteria for SAEs will be captured on the appropriate case report form (CRF). Information to be collected includes event description, time of onset, clinician's assessment of severity, relationship to study product (assessed only by those with the training and authority to make a diagnosis), and time of resolution/stabilization of the event. All AEs occurring while on study must be documented appropriately regardless of relationship. All AEs will be followed to adequate resolution.

Any medical condition that is present at the time that the participant is screened will be considered as baseline and not reported as an AE. However, if the study participant's condition deteriorates at any time during the study after enrollment, it will be recorded as an AE.

Changes in the severity of an AE will be documented to allow an assessment of the duration of the event at each level of severity to be performed. AEs characterized as intermittent require documentation of onset and duration of each episode.

At each study visit, the investigator will inquire about the occurrence of AE/SAEs since the last visit. Events will be followed for outcome information until resolution or stabilization.

If a diagnosis is clinically evident (or subsequently determined), the diagnosis rather than the individual signs and symptoms or lab abnormalities will be recorded as the AE.

All solicited (see **Table 12** below) and unsolicited AEs will be recorded through Day 7 after each injection. Injection site reactions will be assessed until Day 7 after injection (PfSPZ Vaccine or normal saline) or until resolved.

After the periods specified above only unsolicited aEs, SAEs, UPs, and new onset of chronic illness (NOCI) will be recorded.

Table 12. Solicited Adverse Events

Laboratory adverse events¹	
Hemoglobin (decreased hemoglobin)	Platelet count (thrombocytopenia or thrombocytosis)
WBC (leukopenia or leukocytosis)	Creatinine (Cr) (increased Cr)
ANC (neutrophil count decreased) or AGC (granulocyte count decreased)	ALT (increased ALT)

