Local reactogenicity (secondary to PfSPZ Vaccine/normal saline) – through Day 7 post injection	
Injection site pain/tenderness	Injection site induration
Injection site erythema/redness	Injection site swelling/edema
Injection site pruritus	Injection site bruising
Limitation of arm movement	
Systemic reactogenicity (secondary to PfSPZ Vaccine/normal saline) – through Day 7 post injection – for children able to express themselves verbally	
Rash	Urticaria
Generalized pruritus	Generalized Edema
Headache	Fever or feverish
Chills	Malaise/Fatigue
Myalgia	Arthralgia
Sweats	Diarrhea
Back Pain	Chest Pain (non-musculoskeletal)
Nausea/Vomiting	Abdominal Pain
Systemic reactogenicity (secondary to PfSPZ Vaccine/normal saline) – through Day 7 post injection – for averbal children	
Rash	Urticaria

Generalized pruritus	Generalized Edema
Drowsiness	Fever or feverish
Inability/refusal to eat or drink	Irritability/fussiness
Nausea/Vomiting	Diarrhea
Symptoms to be solicited during malaria monitoring phase – study days 43 through 211	
Headache	Chills/rigors
Malaise/fatigue	Dizziness/lightheadedness
Myalgias/arthalgias	Fever or feverish

¹ Note absolute lymphocyte counts and absolute eosinophil counts will be captured on CRFs for use for research assessments. If clinically significant changes as determined by PI, these may also be reported as AEs.

Any laboratory abnormalities (other than those specified as safety labs in the protocol as defined by the values in the toxicity table) should be reported as AEs if they require intervention. Interventions include, but are not limited to, discontinuation of treatment, dose reduction/delay, additional assessments, or concomitant treatment. In addition, any medically important laboratory abnormality may be reported as an adverse event at the discretion of the investigator. This could include a laboratory result for which there is no intervention, but the abnormal value suggests a disease or organ toxicity. In addition, similar to solicited AEs, all laboratory AEs will be collected and graded for severity through 7 days after each vaccination until resolved.

The Investigator will assess all AEs with respect to **Seriousness** (criteria listed above), **Severity** (intensity or grade), and **Causality** (relationship to study agent and relationship to research) according to the following sections in the protocol.

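### Section 9.11.4 ends laboratory AE recording 7 days after each dose, although the post-dose-2 and post-dose-3 safety panels are drawn at about day 14

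*Protocol*

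**What the plan says.** Four parts of the protocol, and the SAP, bear on when laboratory abnormalities count.

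- **Collection rule, Section 9.11.4.** For the laboratory tests, "all laboratory AEs will be collected and graded for severity through 7 days after each vaccination until resolved". Earlier in the same section, all solicited events (Table 12, Solicited Adverse Events) "and unsolicited AEs will be recorded through Day 7 after each injection". Table 12 includes hemoglobin, WBC, neutrophils, platelets, creatinine and ALT. The section then adds: "After the periods specified above only unsolicited aEs, SAEs, UPs, and new onset of chronic illness (NOCI) will be recorded".
- **Secondary endpoint, Sections 2.1 and 4.** The arms are compared on the proportions "experiencing laboratory abnormalities from time of V1 to 14 days after V3".
- **Pausing rule** (headed 7.1.1, inside Section 8.1). The laboratory criterion counts vaccinees who "experience the same grade 3 laboratory abnormality on day V2 + 14 or day V3+14".
- **Schedule of Activities, Section 2.3.** Post-dose CBC and ALT/creatinine draws fall on Day 8, Day 22 and Day 43.
- **Analysis, Protocol Section 10.4.2 and SAP Section 3.1.** Both summarise clinically relevant abnormalities recorded in the 14 days after V3.

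**The concern.** The window in which a laboratory result becomes a graded AE should contain the visits at which the blood is drawn. Here it appears not to for two of the three doses. An abnormality first seen on Day 22 or Day 43 arises after Section 9.11.4 has closed its laboratory window. The words about following events until resolution do not help: they prolong follow-up of an abnormality already found and do not admit a new one.

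The remaining routes in Section 9.11.4 are weak for these tests. The instruction to report abnormalities that need intervention sets aside the protocol safety labs. What is left is a permission, at the investigator's discretion, to report medically important results. A comparison of proportions between arms should not rest on discretionary capture.

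The dose-2 panel has particular weight. The text introducing the pausing rule notes that this is only the second study giving children two priming doses a week apart, and for that reason stresses safety labs after the second dose.

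**Working it through.** **1. Reproduce the stated time points.** V1 is Day 1, V2 Day 8 and V3 Day 29 (Section 2.3).

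- Post-V1 panel: 8 − 1 = 7 days
- Post-V2 panel: 22 − 8 = 14 days
- Post-V3 panel: 43 − 29 = 14 days

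The last two match the pausing rule's V2+14 and V3+14. The schedule row for time since the last dose reads "Days post last PfSPZ Vaccination - - - - 0 2 0 2 4 5 6 14 0 3 7 NA". It shows 0 at Day 8 because V2 is given then, and 14 at Day 22.

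**2. Confirm which days carry a panel.** The columns of Table 1 are displaced in the text available, so I checked placement from the daily blood totals ("6.5 12.5 0 0 3 0 2 0 0 0 0 13.5 1 11.5 0 5.5" for Table 1; 13.5 mL for Day 43 in Table 2). A full panel is 0.5 mL for CBC plus 0.5 mL for ALT/creatinine, or 1.0 mL.

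| Day | Total (mL) | Other scheduled tubes (mL) | Left for panel (mL) |
|---|---|---|---|
| 1 | 3 | 0.5 + 0.5 + 1 = 2 | 1.0 |
| 8 | 2 | 0.5 + 0.5 = 1 | 1.0 |
| 10 | 0 | 0 | 0 |
| 22 | 13.5 | 0.5 + 0.5 + 5 + 5 + 1 + 0.5 = 12.5 | 1.0 |
| 29 | 1 | 0.5 + 0.5 = 1 | 0 |
| 32 | 11.5 | 10 + 1 + 0.5 = 11.5 | 0 |
| 43 | 13.5 | 0.5 + 0.5 + 5 + 5 + 1 + 0.5 = 12.5 | 1.0 |

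The Day 1 draw is a conditional pre-dose repeat ("These labs will be repeated prior to V1 if drawn 28 days or more before V1 is scheduled"). The full post-dose panels are therefore Days 8, 22 and 43. The later hemoglobin-only draw in Table 2 is not counted.

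**3. Apply the visit windows** (Day 8: −1/+3; Days 22, 29 and 43: ±3).

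- Post-V1: Day 7 to Day 11, so 6 to 10 days after V1.
- Post-V2: with V2 on Day 8, 14 ± 3 = 11 to 17 days. If V2 also moves within its window, 19 − 11 = 8 to 25 − 7 = 18 days.
- Post-V3: timed from the actual V3, 14 ± 3 = 11 to 17 days. On a fixed calendar, 40 − 32 = 8 to 46 − 26 = 20 days.

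The smallest gap after V2 or V3 is 8 days, so neither panel can fall within 7 days when doses and visits are in window. The post-V1 panel is inside nominally but can run to day 10.

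**4. Set the windows side by side, read literally at nominal days.**

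| Panel | 9.11.4 (≤ 7 days) | Pausing rule | Endpoint (V1 to V3+14) | 10.4.2 / SAP 3.1 (14 days after V3) |
|---|---|---|---|---|
| Day 8 (V1+7) | in | not named | in | out |
| Day 22 (V2+14) | out | named | in | out |
| Day 43 (V3+14) | out | named | in | in |

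On this reading the collection rule and the analysis sentence share no scheduled panel. A Day 43 visit held at +3 days is V3+17, which is 17 − 14 = 3 days past the end of the endpoint.

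**The case against.** A reader might infer that the laboratory endpoint would hold data after dose 1 only, and that both panels used by the pausing rule would go ungraded. The documents do not support either conclusion.

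- The endpoint is defined on laboratory abnormalities, not on AE forms completed under Section 9.11.4. Section 11.8.1 lists clinical laboratory data separately from adverse events as data to be entered, so the Day 22 and Day 43 values would exist in the database.
- The pausing rule counts Grade 3 results at V2+14 and V3+14. It cannot be operated without grading those panels, and it is more specific than the general sentence. The Appendix A laboratory grading table carries no time limit.
- Section 9.11.4 also requires all AEs on study to be documented and continues unsolicited AEs after Day 7. In Table 12 the local and systemic headings carry a Day 7 limit and the laboratory heading does not, which suggests that no laboratory cap was intended.

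All of this stands, and it shows the likely intent. It does not reconcile the text. Section 9.11.4 states the 7-day limit specifically for laboratory AEs and places the safety labs among events recorded to Day 7. A site could record a Day 22 abnormality as a laboratory AE, as an unsolicited AE, at its discretion, or not at all, and cite the protocol each time.

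**Conclusion.** The inconsistency is real. Two of the three nominal post-dose safety panels (67%) fall outside the stated laboratory AE window, and the third can miss it. What is at risk is uniform recording and grading of these results as AEs; loss of the endpoint data is not shown. Because site staff are blinded, discretionary capture should not systematically favour one arm. The likelier effects are under-recording and counts that are not comparable between doses.

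This rests on three assumptions. Doses and visits are in window; a dose delayed beyond its window could change the gaps. The Day 8 panel is placed partly from blood volumes, whereas the pausing rule independently supports the other two time points. The Day 8 sample is attributed to dose 1 and drawn before V2, following the order of steps in Section 9.3; by date alone, a late Day 8 draw could be counted as day 0 after V2.

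**What to change.** 1. In Section 9.11.4, amend both statements: the one limiting Table 12 solicited events to Day 7 and the laboratory sentence. Take laboratory AEs out of the limit. State that they are collected and graded from V1 through the scheduled V3+14 panel, or the equivalent panel after the last dose received, including every scheduled safety panel drawn within its visit window. Changing only the laboratory sentence would leave the other limit in force.
2. In the endpoint (Sections 2.1 and 4), in Section 10.4.2 and in SAP Section 3.1, state that the V3+14 visit counts when drawn within its ±3-day window, and that all panels from V1 are summarised.
3. Leave the 7-day period for local and systemic reactogenicity as it is.

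The cost is a few sentences across the protocol and SAP and a matching line in the CRF completion guideline. No blood draw is added, and no grading threshold or pausing criterion changes. Section 8.2 lets safety labs be deferred once vaccination stops, so the wording for children who stop early should say which panel, if any, closes their window.

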9.11.5 Adverse Event Reporting

Line listings, frequency tables and other summary AE data will be submitted to the IND sponsor when needed for periodic safety reviews, review of IND annual reports, review of IND safety reports, and preparation of final study reports.

The study sponsor will be responsible for notifying the Food and Drug Administration (FDA) of any unexpected fatal or life-threatening suspected adverse reaction as soon as possible, but in no case later than 7 calendar days after the sponsor's initial receipt of the information. In addition, the sponsor must notify FDA and all participating investigators in an Investigational New Drug (IND) safety report of potential serious risks, from clinical trials or any other source, as soon as possible, but in no case later than 15 calendar days after the sponsor determines that the information qualifies for reporting.

9.11.7 Events of Special Interest

Seizures of any severity will be considered an event of special interest and will be reported to the IND sponsor and FMPOS on the NIH Reportable Events Form sent by fax or email attachment no later than 7 calendar days of site awareness of the event.

All UPs that are also adverse events will be reported to the IND sponsor on the NIH Reportable Events Form sent by fax or email attachment no later than 7 calendar days of site awareness of the event.

UPs that are not AEs will also be reported to the IND sponsor.

